3.4 Withdrawal from the study

Participants will have the right to withdraw from the study for any reason at any time. This will not affect their staff position on the PALM-007 study. People who have had a serious allergic reaction to the first dose of MVA-BN will not receive a second study dose but will be followed as described in section 4.2. If participants had a previous serious allergic reaction to any of the components of MVA-BN prior to joining this study, they may be at increased risk of serious allergic reactions. Therefore, these participants will be excluded from the study.

If a participant develops monkeypox infection, he/she will be withdrawn from the study and will receive the best treatment available for this disease. If this occurs between the first and second dose of vaccine, the participant will not receive the second dose.

If a participant decides to withdraw from the study, no further data will be collected about him/her. However, data collected up to the time of withdrawal will be used in analyses.

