4.2. Follow-up of participants

Participants will be followed until 28 days after the second dose of vaccine. Follow-up visit will be done either in person at INRB (in Kinshasa) and at the Monkeypox treatment centers in the PALM-007 study or by phone calls on Day 3, Day 14, and Day 28 post each vaccination. Study participants will be provided with contact information of vaccine research staff and have the right to contact the research team either directly or by phone if they have any questions about post-vaccination reactions they may be experiencing or if they are concerned. There is a window of +/- one day for each visit except the day of the second dose which can be done on day 28 after the first dose with a window of +7 days. This second dose must not be given before day 28. During each visit, participants will be asked to report to the research team AEs via open-ended questions. All SAEs will be followed-up. SAEs that have not resolved by the end of the per-protocol follow-up period for the subject (Day 28 after second dose) are to be followed until final outcome is known (to the degree permitted by the IRB-approved informed consent form). If it is not possible to obtain a final outcome for an SAE (e.g., the participant is lost to follow-up), the last known status and the reason a final outcome could not be obtained will be recorded by the investigator on an SAE report update and the CRF.

On the day of administration of the second dose of vaccine, vital signs, and physical examination will be done to all participants and a pregnancy test will be done on all women

of childbearing potential prior to vaccine administration. If the pregnancy test is positive, the second dose will not be given, and the participant will be followed up as described in [section 3.5](#). Participants will be instructed to report any AEs that are experienced outside of the protocol defined follow up days. The reporting form of the national pharmacovigilance system of the DRC will be used for reporting. The research team will complete the notification form which will be sent to the National Pharmacovigilance Center (CNPV) by e-mail (scanned copies).

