All records will be kept confidential to the extent provided by local laws in the jurisdictions in which the study is conducted. Study monitors and other authorized individuals may inspect all documents and records required to be maintained by the investigator, including but not limited to, medical records. Records will be kept locked, and data will be coded. Any personally identifiable information maintained for this study will be kept on restricted-access computers and networks. Personally identifiable information will only be shared with individuals authorized to receive it under this protocol. Individuals not authorized to receive personally identifiable information will be provided with coded information only, as needed. Clinical information will not be released without written permission of the participant, except as necessary for monitoring by the IRB/EC, NIAID, local regulatory agencies, the pharmaceutical supporter, or other authorized individuals.

The confidentiality of all participants will be protected in accordance with Good Clinical Practice.

Compensation

Participants will be vaccinated at the workplace; no compensation will be provided. However, if there is a need for an unscheduled visit, compensation of \$5 US will be provided for transportation. During follow-up of pregnancies, and if necessary, the site may assist the pregnant women in the fees related to antenatal consultation and ultrasounds. A maximum of \$5 may be given to the participant for each prenatal consultation and a maximum of \$10 for each ultrasound.

8. Statistical Considerations

The study will vaccinate 1000 participants to estimate the following:

- 1) The frequency and severity of solicited SAEs up to 14 days after each dose of the vaccination.
- 2) The frequency and severity of AEs from the first vaccine dose to 28 days after the second vaccine dose.

Statistical analysis

The proportion of SAEs will be estimated along with 95% confidence intervals using the Clopper-Pearson method at:

- 14 days after the first vaccine administration, and
- 28 days after the vaccine boost.

The proportion of AEs will be estimated along with 95% confidence intervals using the Clopper-Pearson method at:

- 14 days after the first vaccine administration, and
- 28 days after the vaccine boost.

The severity of events will be tabulated and analyzed for reporting.

Sample size justification

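### Section 8 does not say how people who leave early without an event count in the AE and SAE proportions; a Kaplan-Meier estimate would settle it at little cost

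*Combined protocol and SAP*

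**What the plan says.** Section 8 (Statistical Considerations) plans for 1000 vaccinated participants ("The study will vaccinate 1000 participants to estimate the following") and gives the same method for both outcomes. For AEs: "The proportion of AEs will be estimated along with 95% confidence intervals using the Clopper-Pearson method at" two times. For SAEs: "The proportion of SAEs will be estimated along with 95% confidence intervals using the Clopper-Pearson method at" the same two times. These are "14 days after the first vaccine administration, and" "28 days after the vaccine boost". With dose 2 given on day 28 to 35, the second time falls about 56 to 63 days after dose 1.

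Section 4.2 sets the planned follow-up: "Participants will be followed until 28 days after the second dose of vaccine". Section 3.4 allows it to end sooner, through voluntary withdrawal (after which data collection stops) or withdrawal because of monkeypox infection. On partial data, section 3.4 says: "However, data collected up to the time of withdrawal will be used in analyses".

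Section 2.2 sets the SAE target as incidence among everyone vaccinated, which is the nearest the protocol comes to naming a denominator. Nowhere does it define an analysis set, a censoring or person-time rule, a missing-data method or an expected loss rate.

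**The concern.** A Clopper-Pearson interval needs a known yes or no for each person at the time point. Someone who withdraws on day 20 without an AE has neither for the post-boost estimate. Three binomial denominators are possible:

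- **All vaccinated.** The leaver counts as event-free, so risk is biased low.
- **Completers plus anyone with a recorded event.** Event-free leavers drop out while leavers with events stay, so risk is biased high.
- **Completers only.** This is unbiased if loss is unrelated to AEs. It removes recorded events of people who left, which sits badly with section 3.4, and it is biased low if people withdraw because of an AE.

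Safety estimation is the study's only objective and section 8 is its whole analysis plan. If the choice is left open, it may be made after the data are seen. Understating risk is the more harmful direction.

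**Working it through.** **1. The plan's own figure.** The sample size justification puts the 95% half-width at no more than 0.05 with 1000 participants. The largest Clopper-Pearson half-width at n = 1000 is 0.0315 (Wald: 1.96 × √(0.25/1000) = 0.0310). With 20% loss, n = 800, it is 0.0352. The statement is correct and is not in dispute.

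**2. Assumed inputs.** The documents give no event rate, timing or loss rate. All of these are assumptions: AE risk 22% in the 3 days after dose 1 and 18% in the 3 days after dose 2; background hazard 0.0035 per day; dose 2 on day 28; a fraction L lost, uniformly over 56 days and independently of AEs.

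- True 56-day risk: 1 − 0.78 × 0.82 × exp(−0.0035 × 56) = 1 − 0.5258 = 0.474.
- True 14-day risk: 1 − 0.78 × exp(−0.0035 × 14) = 0.257.

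**3. Bias with all vaccinated as denominator.** An event at day t is seen with probability 1 − L·t/56, so the shortfall is L × ∫(t/56) dF(t) = L × (mean event-free time within 56 days ÷ 56 − S(56)). With S the event-free probability, the mean event-free time is 2.64 + 18.48 + 1.91 + 13.74 = 36.77 days (days 0–3, 3–28, 28–31, 31–56). The bracket is 36.77/56 − 0.5258 = 0.131. The shortfall is 0.131 × L.

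**4. Completers plus events.** With c the all-vaccinated proportion from step 3, the estimate is c ÷ [c + 0.5258 × (1 − L)].

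| Loss | All vaccinated (coverage of 95% interval) | Completers plus events (coverage) | Completers only | Kaplan-Meier |
|---|---|---|---|---|
| 5% | 46.8%, 0.7 points low (93%) | 48.4% (92%) | 47.4% | 47.4% |
| 10% | 46.1%, 1.3 points low (88%) | 49.4% (78–79%) | 47.4–47.5% | 47.4–47.5% |
| 20% | 44.8%, 2.6 points low (63%) | 51.6% (32–33%) | 47.4% | 47.4% |

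Coverage is from simulation with n = 1000 and 2000 to 3000 replicates. Completers-only and Kaplan-Meier intervals (the latter log-log) kept about 95%. With no loss, all four methods agree.

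**5. A different event pattern.** Take a true risk of 30% with constant hazard λ and exponential loss at rate μ. The all-vaccinated value is λ/(λ+μ) × (1 − exp(−(λ+μ)T)). At 10% loss, λT = 0.3567 and μT = 0.1054, so it is 0.772 × (1 − 0.7 × 0.9) = 0.286. The values are 0.293, 0.286 and 0.271 at 5%, 10% and 20% loss. If all events fall in days 0–3, the 20% figure is 0.298.

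**6. Where it hardly matters.** For AEs at day 14 in the step 2 scenario with 20% loss, the all-vaccinated value is 25.5% against 25.7%, with 95% coverage. For a 1% SAE risk at 20% loss, it is 0.90% to 0.99%, and coverage is at least 96.6%.

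**7. Loss related to AEs.** Suppose 5% independent loss and, in addition, 10% of people with an AE withdrawing after it. Completers only then gives 0.474 × 0.9 ÷ (0.474 × 0.9 + 0.526) = 44.8%, with simulated coverage of 66–68%. Kaplan-Meier stays at 47.4–47.5%, because the event is recorded before the person leaves.

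**The case against.** The strongest reply is that the defect is an unstated denominator and that one clarifying line would cure it. Much of that case stands.

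- A reader might infer that the plan scores leavers as event-free and is therefore biased low. The documents do not say so. That scoring follows from one reading, the most natural one, and another reading biases upward.
- A reader might also infer that no binomial denominator can work. Not so: completers only is valid when loss is unrelated to AEs (step 4). Section 3.4 does not require every person in every proportion; someone leaving on day 30 still contributes at day 14.
- Section 4.2's phrase "the participant is lost to follow-up" concerns the final outcome of an SAE already reported. It does not forecast event-free loss. A monkeypox case is itself an AE under section 4.3.1, so that withdrawal is not event-free for the AE estimate.
- Loss may well be low. Participants are study staff vaccinated at the workplace, people who cannot be reached by phone are excluded, and follow-up lasts about eight weeks.
- If the post-boost estimate is restricted to dose-2 recipients and starts at dose 2, the crude value at 20% loss is 25.1% against 25.7%, with 94% coverage. That removes most of the bias without Kaplan-Meier.
- The simulations used a log-log interval, not the beta product interval proposed here.

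What does not fall away is step 7: the one unbiased binomial reading fails once people withdraw after a reaction, and it drops events that were recorded.

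**Conclusion.** The point holds as a gap with a cheap and better alternative. It is not a demonstrated bias in the plan. Section 8 leaves the handling of incomplete follow-up open, and the choice matters mainly for AEs to 28 days after the boost. Under the assumed inputs, the all-vaccinated reading is low by about 0.7, 1.3 and 2.6 points at 5%, 10% and 20% loss. At 20% loss the two biased readings differ by 51.6 − 44.8 = 6.8 points, more than twice the maximum half-width of 3.1 points. At 2% loss the effect is negligible (0.131 × 0.02 = 0.3 points). It is also negligible at day 14 and for rare SAEs. These sizes rest wholly on assumed event rates, timing and loss, and on loss independent of AEs except in step 7. A general claim that the planned intervals lose their 95% coverage is not supported.

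**What to change.** Replace the two Clopper-Pearson statements in section 8 with text along these lines:

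- The cumulative incidence of a first AE, and separately of a first SAE, is estimated at each time point as 1 minus the Kaplan-Meier estimate. Participants without the event are censored at their last completed contact. 95% intervals use the beta product confidence procedure, which equals Clopper-Pearson when nobody is censored.
- The time origin is stated for each estimate: from dose 1 among all vaccinated, and from dose 2 among dose-2 recipients. This also settles where people who never receive dose 2 belong.
- A visit completed within its one-day window counts as follow-up to the nominal day. Otherwise a final visit one day early would be treated as censoring.
- The number still under observation is reported at each time point.

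The cost is a change of wording and a few lines of code. AE assessments are already scheduled at every visit, but AE onset and last-contact dates must be recorded. Intervals widen slightly under censoring. Censoring must still be assumed non-informative for people who leave before any event.

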3.2. Study population

Participants 18 years and older will be recruited from personnel of the PALM-007 Monkeypox study and staff associated with the study in the DRC. Participation in the study will be voluntary and up to 1000 participants may be enrolled at the PALM-007 study sites or in Kinshasa.

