The sample size was determined according to the expected number of staff to be vaccinated, in addition to ensuring adequate precision of 95% confidence intervals of the estimates of the frequency of SAEs and AEs. With 1000 participants, the expected halfwidth of the confidence interval will not be greater than 0.05.

9. Schedule of activities

Table 9.1 Schedule of Activities

Evaluation/Procedure	Screen	Follow-up						
		1	2	3	4	4.1	5	6
Visit	1							
Day	0	3±1 ^b	14±1 ^b	28±1 ^b	28+7	3±1 ^c	14±1 ^c	28±1 ^c
Informed consent	X							
Eligibility (inclusion/exclusion) assessment	X							
Demographics	X							
Medical history	X							
Medication review	X	X	X	X	X	X	X	X
Weight and Height	X							
Pregnancy test (serum or urine)*	X				X			
Vital Signs	X				X			
Physical examination	X				X			
Vaccination	X				X			
Assessment of AEs/SAEs	X	X	X	X	X	X	X	X

^b Days after First dose of vaccine.

^c Days after second dose of vaccine

* Pregnancy test for women of childbearing potential

10. Abbreviations

ACOREP	Autorité Congolaise de Réglementation pharmaceutique
DNA	DesoxyriboNucleic Acid
CEF	Chicken Embryo Fibroblasts
EC	Ethics Committee
CEM	Cohort Event Monitoring
CNPV	Centre National de Pharmacovigilance
CRF	Case report Form
CTCAE	Common Terminology Criteria for Adverse Events
AE	Adverse Event
SAE	Serious Adverse Event
EMA	European Medicines Agency
ESP	Ecole de Santé Publique
FDA	Food and Drug Administration
GCP	Good Clinical Practices
ICH	International consil on harmonization
INRB	Institut National de Recherche Biomédicale
IRB	Institutional review board
MVA-BN	Modified Vaccinia Ankara-Bavarian Nordic
NIAID	National Institute of Allergy and Infectious Diseases
OCPRO	Office of Clinical Research Policy and Regulatory Operations
OHRP	Office for Human Research Protections
WHO	World health Organization
PALM	Pamoja Tulinde Maisha
IP	Investigational Product
PV	Pharmacovigilance
DRC	Democratic Republic of the Congo
TFF	Tangential Flow Filtration

11. References

1. WHO Smallpox Eradication programme. Vaccines and immunization for monkeypox. 2022. p. 1–28.
2. U.S. Food and Drug Administration. Package Insert JYNNEOS [Internet]. 2022 [cited 2022 Oct 6]. p. 1–11. Available from: chrome-extension://efaidnbmnnibpcajpcglclefindmkaj/https://www.fda.gov/media/131078/download

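### Does a half-width bound of 0.05 at 1000 participants misstate the precision of the study?

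*Combined protocol and SAP*

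**What the plan says.** Section 8 (Statistical Considerations) opens with a fixed number: "The study will vaccinate 1000 participants to estimate the following". Section 3.2 (Study population) words the same number as a ceiling: "up to 1000 participants may be enrolled at the PALM-007 study sites or in Kinshasa".

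Under the statistical analysis heading, Section 8 names the same interval method for both outcomes: "The proportion of SAEs will be estimated along with 95% confidence intervals using the Clopper-Pearson method at" two time points, and likewise "The proportion of AEs will be estimated along with 95% confidence intervals using the Clopper-Pearson method at" the same two.

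The sample size justification gives two grounds. The first is practical: "The sample size was determined according to the expected number of staff to be vaccinated". The second, added to it, is "ensuring adequate precision of 95% confidence intervals of the estimates of the frequency of SAEs and AEs". The only number supporting the second ground is "With 1000 participants, the expected halfwidth of the confidence interval will not be greater than 0.05". The plan gives no expected SAE or AE rate, no probability of detecting a rare event, no limit for the case of zero events and no allowance for dropout.

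**The concern.** In a one-arm safety cohort without a comparator or a hypothesis test, interval width is the only quantitative property of the design. A reader who recomputes it finds that 0.05 is not the worst-case value at 1000 participants. That raises the suspicion that the figure was worked out for another sample size or by another method.

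The figure is also meant to cover SAEs, whose incidence is the first specific objective in Section 2.2. If SAEs are rare, a bound of 5 percentage points does not tell an ethics committee what rate the study could exclude or would be likely to reveal. Finally, the sentence is tied to 1000 participants, although Section 3.2 allows fewer. If the claim were false, or if a decision hung on it, the justification of the sample size would need repair.

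**Working it through.** **Inputs from the plan.** n = 1000 (Section 8; a ceiling in Section 3.2); two-sided 95% Clopper-Pearson intervals (Section 8); stated bound 0.05 (sample size justification).

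**Formula.** For x events in n participants, the lower limit is the 0.025 quantile of Beta(x, n − x + 1), and 0 if x = 0. The upper limit is the 0.975 quantile of Beta(x + 1, n − x), and 1 if x = n. The half-width is (upper − lower)/2.

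**Can 0.05 be reproduced at n = 1000?**
- Largest exact half-width over all x: 0.03145. The expected half-width at a true proportion of 0.5 is 0.03144.
- Normal approximation at 0.5: 1.96 × √(0.25/1000) = 0.0310.
- Longer arm of the exact interval: 0.0315.
- Bonferroni over four intervals: 0.0399. 99% level: 0.0411. Full width: 0.0629.

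None of these equals 0.05, so it is not the value at n = 1000. As an inequality the claim holds: 0.0315 ≤ 0.05, with a ratio of 0.05/0.0315 = 1.6.

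**Where does 0.05 become the worst case?** The exact maximum is 0.05003 at n = 401 and 0.04997 at n = 402. The normal approximation gives 1.96² × 0.25/0.05² = 384.2, so 385.

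**Does the bound survive lower enrolment?**

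| Participants | Largest exact half-width | Upper 95% limit if no SAE is seen, 1 − 0.025^(1/n) |
|---|---|---|
| 1000 | 0.0315 | 0.37% |
| 700 | 0.0377 | 0.53% |
| 500 | 0.0447 | 0.74% |

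The bound holds in every row.

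**What does the design give for rare SAEs?** The plan states no SAE rate, so the rates here are assumptions. At n = 1000 the expected exact half-width is 0.0027 at a true rate of 0.1%, 0.0049 at 0.5% and 0.0067 at 1%. The stated bound is therefore about 7 times (0.05/0.0067) to 19 times (0.05/0.0027) wider than what would be seen. The chance of at least one SAE is 1 − (1 − p)^1000. It is 63% at p = 0.1%, and it reaches 95% at p = 1 − 0.05^(1/1000) = 0.30%.

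**What will the planned analysis report?** Exact 95% intervals at n = 1000 are 0 to 0.37% for 0 events, 0.003% to 0.56% for 1, 0.16% to 1.16% for 5 and 0.48% to 1.83% for 10. They come from the method already named and do not involve 0.05.

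**The case for a change.** The best argument for a change is that precision is offered as a ground for the sample size, for SAEs as well as AEs, and that its only number fails to inform on SAEs. A reader may take worst-case AE precision to be 1.6 times poorer than it is. The looseness also hides what is lost if enrolment falls short. With a true SAE rate of 0.1%, the chance of seeing at least one is 63% at 1000 participants, 50% at 700 (1 − 0.999^700) and 39% at 500 (1 − 0.999^500), yet the same 0.05 covers all three. Better figures would cost one sentence and a short table.

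Part of this stands. The bound is loose, and it says nothing useful about a rare proportion. The fixed number in Section 8 and the ceiling in Section 3.2 are worded differently.

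The rest does not carry a change. The plan never says that the half-width equals 0.05, so a true conservative bound is not an error of arithmetic. Nor does it derive 1000 from a 0.05 target, so showing that 402 would suffice does not undermine a number set first by the size of the workforce. The aim for SAEs is to estimate incidence, without a detection target that the study could miss. The difference in wording about 1000 is clerical: the intervals will be computed from the participants actually vaccinated, whichever wording is read.

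**Conclusion.** No change to the plan is called for. The stated bound is correct: the worst-case exact half-width is 0.0315 at 1000 participants and stays below 0.05 at any analysed number from 402 upwards. The statement is loose by a factor of 1.6 in the worst case, and by about 7 to 19 at assumed SAE rates of 1% down to 0.1%, which are not taken from the plan.

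That looseness has no consequence for the results. Enrolment follows staff numbers, the interval method is fixed, and no test, threshold or stopping decision refers to 0.05. A study run exactly as written would give the same estimates, intervals and conclusions with a sharper sentence in its place. The conclusion assumes that at least 402 participants are analysed and that the intervals are calculated as Section 8 describes. The authors may choose to quote 0.032 and the zero-event limit of 0.37% when reporting, as a courtesy to readers.
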